6.2 Sample Size Determination

For the initial phase of this study we anticipate enrolling 20 patients (DHMC treats about 80-100 SRS patients yearly): 5 with resected lesions up to 2.0 cm (diameter), 5 with intact lesions up to 2.0 cm, 5 with resected lesions greater than 2.0 cm, and 5 with intact lesions greater than 2.0 cm. Based on a median event-free survival time of 6 months in the control group, a log-rank test with a one-sided significance level of 0.05 and a power of 0.80 can detect a relative risk of 0.39 or smaller. Thus, we have sufficient power to detect 61% increase in the risk of toxicity, recurrence or death.

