Parameter	% for all subjects		% of subgroup with tumors below or above cutoff size of 3.0 cm				% of subgroup with tumors below or above cutoff size of 2.0 cm			
	1 y	2 y	Below or equal to 3.0 (n=29)		Above 3.0 (n=20)		Below or equal to 2.0 (n=15)		Above 2.0 (n=34)	
			1 y	2 y	1 y	2 y	1 y	2 y	1 y	2 y
Overall survival	52.5	31.7	51.3	36.0	55.0	30.0	69.2	49.5	46.6	25.1
Free of LR	85.5	66.9	89.1	89.1	80.7	40.4	100.0	100.0	79.2	51.3
Free of DR	43.8	24.4	50.0	36.4	35.6	8.9	81.8	65.5	31.5	10.5
Free of ICR	41.4	17.7	45.4	31.1	35.6	5.9	81.8	65.5	28.3	4.2
Free of WBRT	58.4	37.3	75.9	65.0	39.9	13.3	100.0	100.0	44.5	20.0

Abbreviations: DR = distant recurrence; ICR = intracranial recurrence (LR or DR); LR = local recurrence; WBRT = whole-brain RT.

Data show estimated 1- and 2-year percentages above and below 3.0 cm (median) and above and below 2.0-cm tumor diameter for the entire sample and for subgroups defined by tumor diameters.

In this trial we will use hyperbaric oxygen as a radiosensitizer prior to stereotactic radiosurgery (SRS) for brain metastases. We hypothesize that reducing tumor hypoxia with HBO will increase the sensitivity of these tumors to SRS, that this clinical benefit should increase with lesion size, and that no significant radiosensitizing effect of HBO will

arise in the surrounding normal brain tissues.

We postulate these hypotheses due to several well-known laboratory phenomena, as demonstrated in the research studies of [name] (co-investigator on this project) and of other investigators:

- tumors are hypoxic;
- HBO increases tissue oxygenation;
- increasing pO_2 levels above hypoxic levels ($pO_2 > 3$ mm Hg) increases radiosensitivity with an OER between 2 and 3;
- this OER effect flattens above 20-30 mm Hg (limiting toxicity in normal tissues).

Several clinical observations also support these hypotheses:

- SRS delivers dose with millimeter accuracy to target tissues, limiting normal tissue toxicity;
- efficacy of SRS for tumors metastatic to the brain decreases when treating larger metastases – for example, >30% local recurrence risk at one year after SRS for lesions >3 cm in diameter versus <20% for lesions <2 cm [8] (Figure 4);
- efficacy of SRS decreases when treating larger resected lesions – for example, DHMC experience demonstrated 51% local control rate observed at two years for resected lesions with diameters greater than 2.0 cm versus 100% local control rate observed for diameters less than 2.0 cm [9] (Table 1).

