For the secondary endpoints, using Cox proportional hazards models, and Kaplan-Meier survival statistics, the overall group of 20 will be analyzed for event-free survival and compared against a matched set of patients from our institution (see below for methodology). This match will be based on tumor size, resection status, and histology-specific graded prognostic assessment (GPA). The GPA is a validated, widely accepted prognostic scale predictive of survival for patients presenting with brain metastases. Diagnosis-specific GPA calculation is based on published criteria including tumor histology, presence of systemic metastases, number of brain metastases, age, performance status, and breast-cancer specific molecular markers [29-31]. Further demographic and treatment data will also be collected, including: gender, subtotal resection versus gross total resection (if tumor resected), tumor diameter (prior to first treatment, whether surgery or SRS), SRS target volume (PTV), and prescribed dose to the PTV. The secondary outcome variables will be the first occurrence of the event of interest and also the time until the first occurrence of the event of interest. These events include: intracranial recurrence at SRS site, intracranial recurrence at a distant site, whole brain XRT, second SRS (classified as either local or distant), third SRS (classified as local or distant), radionecrosis at the SRS site, and death.

A retrospective database pertaining to Dartmouth-Hitchcock's experience with stereotactic radiosurgery in the treatment of brain metastases is being collected through Study 00030625 (PI [name]). Pertinent matching variables, along with demographic variables, treatment variables, and outcome variables for the control population are available on 00030625. The matching variables (histology, lesion size, resection status, and calculated GPA) will be used to identify a control population in the Study 00030625 that match 1:1 against the D12129 enrolled patient population.

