Specifically, patients with similar tumor histologies will be matched against histologies found in the D12129 patient population, falling into one of six categories: (1) non-small cell lung cancer, (2) melanoma, (3) breast cancer, (4) renal cell cancer, (5) GI cancers, and (5) other histologies. Once a histologic match is identified, the patient is then matched by resection status (either unresected or resected). The third matching variable is then GPA. If an exact GPA match is not available in the 000030625 data base, then a patient with a higher GPA will be selected, with the control patient's GPA as near as possible to that of the corresponding D12129 patient (thereby, if anything, biasing the survival outcome data slightly against the D12129 data set). Lastly, the fourth matching variable is tumor size (i.e. maximum tumor diameter) at time of treatment (a categorical variable, either below or above 2.0 cm). If an exact match for the fourth variable is not available in the 000030625 data base, then size will be matched as closely as possible to the 2.0 cm cut-off from those patients available in this historical database. These

matching patients identified in 000030625 data base will serve as the control group for the D12129 study.

Once the control group patients have been selected, their data will be extracted from the 000030625 database in de-identified form. These data will be reviewed by an “honest broker” to assure proper de-identification and HIPAA compliance. These de-identified control group data will then be merged with the D12129 dataset. Analysis of this combined data base then will allow comparison of HBO-treated and control patients in terms of event-specific outcome parameters, with events including: death, local intracranial recurrence, distant intracranial recurrence, whole brain radiation therapy, and repeat SRS (either local or distant).

Exploratory variables will include QOL data and tumor markers. Comparisons for change in markers before versus after HBO-SRS treatment will be performed for the entire group of twenty patients. Also comparisons will be performed for subgroups (including comparisons of those with resections versus those without, and of those above 2.0 cm diameter versus those below).

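### The log-rank comparison is sized as one homogeneous group and not stratified by the 2.0 cm class; on Table 1 rates its power at a relative risk of 0.39 is roughly 55–66%, and stratifying recovers much of the gap to 80%

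*Combined protocol and SAP*

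**What the plan says.** Section 6.2 plans 20 patients in four cells of five: "5 with resected lesions up to 2.0 cm (diameter), 5 with intact lesions up to 2.0 cm", and the same again above 2.0 cm. Half of the group therefore has small lesions. The same paragraph sizes the comparison with controls on a single figure: "Based on a median event-free survival time of 6 months in the control group". From this it concludes that a one-sided 5% test would have 80% power if the relative risk were 0.39. It gives no source for the 6 months and no length of follow-up. Its closing sentence counts toxicity as an event alongside recurrence and death.

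Section 6.1 draws controls from the institution's SRS database (Study 00030625) to "match 1:1 against the D12129 enrolled patient population". The matching variables are histology, resection status, GPA and, last, tumor size, which is "a categorical variable, either below or above 2.0 cm". If no exact size match exists, the nearest available is taken. The analysis is by Cox models and Kaplan-Meier methods, with no stratification or pairing stated.

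Table 1 (Section 1.1) gives 1- and 2-year outcomes for 49 resected DHMC patients, 15 at or below 2.0 cm and 34 above.

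**The concern.** The plan treats the 2.0 cm class as important enough to fill quotas by it and to match on it, and its background argues that size drives outcome. The test is then sized as if every control had the same hazard. When two classes with very different hazards are pooled in an unstratified log-rank test, early events come mostly from the high-risk class and late events from the low-risk class. A treatment effect that is constant within each class is then diluted in the pooled comparison. Detecting 0.39 with 80% power is the only operating characteristic given for the comparison with historical controls, so an overstatement there misleads anyone who judges what that comparison can show.

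**Working it through.** **Inputs.** From 6.1 and 6.2: 20 v 20, one-sided 0.05, relative risk 0.39, control median 6 months, 10 + 10 by size class. From 6.1 and 5.4: accrual over 36 months, follow-up of at least one to two years, protocol visits to two years. From Table 1 (1 year / 2 years):
- overall survival 69.2 / 49.5% (≤2.0 cm) and 46.6 / 25.1% (>2.0 cm);
- free of intracranial recurrence 81.8 / 65.5% and 28.3 / 4.2%.

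I take 0.39 as the hazard ratio, HBO to control. The next sentence of 6.2 restates it as an increase in risk, which is a separate matter.

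**1. The plan's own figure.** With exponential survival and 24 months per patient, the control event probability is 1 − 0.5^(24/6) = 0.9375 and the HBO one is 1 − 0.5^(0.39 × 24/6) = 0.661. Expected events are 20 × (0.9375 + 0.661) = 32.0. Freedman: √32.0 × 0.61/1.39 − 1.645 = 0.84, so power is 0.80. Schoenfeld gives 0.845. The stated 80% reproduces on its own inputs.

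**2. Size-specific event-free survival.** The documents give no joint rate for recurrence or death, so I use two cases.
- Independence (product), 1 year: ≤2.0 cm 0.818 × 0.692 = 0.566; >2.0 cm 0.283 × 0.466 = 0.132; half of each 0.349. At 2 years: 0.655 × 0.495 = 0.324 and 0.042 × 0.251 = 0.011.
- Full overlap (the smaller of the two figures), 1 year: 0.692 and 0.283, mean 0.488. At 2 years: 0.495 and 0.042.

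On the product rates the class medians are 12 ln 2 / −ln 0.566 = 14.6 months and 12 ln 2 / −ln 0.132 = 4.1 months. The half-and-half mixture has a median of about 7.3 months, or 7.9 if one exponential is fitted to 0.349. On the overlap rates the mixture median is about 11.5 months.

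**3. Changing the median alone (product rates, 24 months).** Moving from 6 to 7.3–7.9 months lowers Freedman power from 0.80 to 0.77–0.76, and Schoenfeld power from 0.845 to 0.82–0.81. This costs a few points.

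**4. Simulated log-rank power.** Relative risk 0.39 within each class, hazards piecewise constant by year, 6,000 runs per entry.

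| Control population and test | Follow-up uniform 12–24 mo | 24 mo | uniform 12–48 mo |
|---|---|---|---|
| One exponential, median 6 months | 0.80 | 0.84 | 0.85 |
| Product, pooled rates, no size difference | 0.73 | 0.78 | 0.80 |
| Product, 10 + 10, unstratified | 0.63 | 0.64 | 0.65 |
| Product, 10 + 10, stratified | 0.74 | 0.78 | 0.79 |
| Overlap, pooled rates, no size difference | 0.65 | 0.72 | 0.73 |
| Overlap, 10 + 10, unstratified | 0.57 | 0.60 | 0.59 |
| Overlap, 10 + 10, stratified | 0.66 | 0.73 | 0.74 |

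Repeat runs shift entries by about two points. Across them the unstratified 10 + 10 rows span about 0.55–0.66, and the stratified product row reaches 0.76 at the shortest follow-up.

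**5. Where the loss comes from.** On the product rates, the change in event rates costs 0.80 − 0.73, 0.84 − 0.78 and 0.85 − 0.80, that is 5–7 points. Ignoring size costs 0.73 − 0.63, 0.78 − 0.64 and 0.80 − 0.65, that is 10–15 points. As a cross-check, the product mixture rescaled to a median of exactly 6 months still has only 0.68 power unstratified at 24 months. On the overlap rates the split is more even: 12–15 points from event rates and 8–14 from ignoring size.

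**6. Gain from stratifying.** Product: 11–14 points. Overlap: 9–15 points.

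**The case against.** The stated 80% is not a slip: it follows from the stated inputs. The alternative rates are thin. The small-lesion figures come from 15 patients, all resected, while half of the planned patients have intact lesions. For intact lesions Section 1.1 gives tumor control by size, which also falls with size, but no event-free survival. Section 6.2 counts toxicity, for which the documents give no rate. As an illustration, an added toxicity hazard of 11–21% per year would bring the half-and-half median to 6.5–5.9 months. Power at 24 months would then be 70–73% unstratified and about 81% stratified, so 6 months may suit the planned mix. Size is the last matching variable and may be matched only approximately, so the controls need not split 10/10. Finally, this is a secondary objective of a proof-of-principle study whose primary endpoint is feasibility.

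All of this stands as a limit on how exactly the shortfall can be stated. It does not remove the structural point: even in the toxicity illustration, stratifying adds 8–11 points (81 − 73 and 81 − 70).

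A reader might go further and infer that the 6 months was taken from Table 1's mix (31% small lesions), and that this wrong median is what takes power from 80% down to the levels above. The documents do not support that. Nothing in them links the 6 months to Table 1. The agreement holds only under independence, where the whole series gives 0.414 × 0.525 = 0.217 at 1 year and a median of about 5.5 months; under full overlap it is about 9.4 months. By the same product-rate simulation, the 31% mix itself has only about 69–71% power unstratified.

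**Conclusion.** The concern holds as a gap in the planned test and its sizing, not as an arithmetic error or a proven wrong median. If events are recurrence or death at Table 1 rates and 0.39 applies within each size class, the unstratified log-rank test has roughly 55–66% power on the planned mix, not 80%. On the product rates most of the loss comes from leaving size out of the test, and the longer control median of about 7–8 months adds only a few points.

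The size of the shortfall is illustrative. It rests on resected-series rates applied to intact lesions, on independence or full overlap of recurrence and death, on successful size matching, on follow-up of at least 12 months, and on leaving out toxicity. It would be too strong to say that the matched controls cannot deliver 80%, because the documents give no rate for the composite that 6.2 names.

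**What to change.** In 6.1, specify that the log-rank test and the Cox model are stratified by the 2.0 cm size class already used for enrolment and matching, with each control classed by its own diameter. In 6.2, replace the single 6-month median with size-specific control rates for the 10/10 mix, preferably from the 00030625 database. State their source, the event definition (including whether toxicity counts) and the follow-up assumed. Then restate the power at 0.39, or the relative risk detectable with 80% power, for the stratified test. The figures above show what to expect but should not be printed as the plan's power. Keep the sample size at 20.

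The cost is a rewording and a short recalculation, with no added patients or data. The downside is that the stated power or detectable effect will probably be somewhat less favourable than it is now.

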2.1.1 Study Objectives

Primary Objective: To demonstrate that coordination of HBO with SRS treatments is feasible.

Secondary Objective: To demonstrate that outcomes for HBO combined with SRS treatment are non-inferior to historical controls.

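### Section 6.2 turns a detectable 61% risk reduction (relative risk 0.39) into a claim of power to detect a 61% risk increase, for which power is only about 40%

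*Combined protocol and SAP*

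**What the plan says.** The calculation in section 6.2 begins: "Based on a median event-free survival time of 6 months in the control group". From this, "a log-rank test with a one-sided significance level of 0.05 and a power of 0.80 can detect a relative risk of 0.39 or smaller". The sentence that follows draws the conclusion: "Thus, we have sufficient power to detect 61% increase in the risk of toxicity, recurrence or death".

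The section plans 20 HBO patients, and section 6.1 selects historical controls to "match 1:1 against the D12129 enrolled patient population", so the comparison is 20 against 20. The secondary objective in section 2.1.1 is: "To demonstrate that outcomes for HBO combined with SRS treatment are non-inferior to historical controls". No non-inferiority margin is given, and section 6.2 holds the only power statement in the plan.

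**The concern.** A relative risk of 0.39 or smaller means that HBO lowers the hazard by at least 1 − 0.39 = 61%. The concluding sentence keeps the 61% and reverses its direction. Power is not symmetric in percentage change. The log-rank test works on the log hazard ratio, where the counterpart of 0.39 is 1/0.39 = 2.56 (a 156% increase). A ratio of 1.61 is a much smaller effect: |ln 1.61| = 0.476 against |ln 0.39| = 0.942.

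Harm is the direction that matters for a claim of non-inferiority. With no margin defined, a reader may take a non-significant comparison, together with this sentence, as good evidence against a 61% rise in toxicity, recurrence or death. Harm is also a live question in the protocol: section 1.5 cites, with caveats, a pooled odds ratio of 2.43 for radiation-related complications when HBO was added in head-and-neck trials.

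**Working it through.** **Inputs.** From section 6.2: one-sided alpha 0.05 (z = 1.645), power 0.80 (z = 0.842), control median 6 months and 20 HBO patients. From section 6.1: 1:1 matching, hence 20 controls, and a minimum follow-up of one to two years. From section 5.4: on-protocol follow-up to two years.

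**Assumptions.** Exponential event times (control hazard ln 2/6 = 0.1155 per month), no loss to follow-up and an unpaired log-rank test. The plan does not say which formula or follow-up produced 0.39, so two standard formulas and a range of follow-up are used.

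**Formulas.**
- Expected events: d = 20(1 − e^(−0.1155F)) + 20(1 − e^(−0.1155·HR·F)), with F the follow-up in months.
- Schoenfeld: power = Φ(√(d/4)·|ln HR| − 1.645); events needed = 4(1.645 + 0.842)²/(ln HR)².
- Freedman: power = Φ(√d·|1 − HR|/(1 + HR) − 1.645).

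**Step 1: reproduce the plan's 0.39.** At HR 0.39 and F = 24, d = 18.75 + 13.22 = 32.0. Freedman power is 79.9%, and the hazard ratio detectable with 80% power is 0.389. Schoenfeld gives a detectable ratio of 0.35 at 12 months, 0.395 at 18 months and 0.42 at 24 months. The 0.39 is therefore sound as a reduction.

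**Step 2: power for a 61% increase (HR 1.61), same design.**

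| Follow-up | Expected events | Schoenfeld | Freedman | Simulated log-rank (20,000 runs) |
|---|---|---|---|---|
| 12 months | 32.9 | 39% | 38% | 39% |
| 24 months | 38.5 | 43% | 42% | 43% |
| 36-month accrual plus 12-month minimum | 38.5 | 43% | 42% | 42% |
| All 40 patients have an event | 40 | 44% | 43% | not run |

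For example, at 24 months √(38.5/4) × 0.476 − 1.645 = −0.167, and Φ(−0.167) = 0.43.

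**Step 3: events needed for 80% power at HR 1.61.** Schoenfeld: 4 × 6.183/0.476² ≈ 109. Freedman: 6.183 × (2.61/0.61)² ≈ 113. The comparison has 40 patients, so longer follow-up cannot close the gap.

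**Step 4: harm that can be detected with 80% power.** Schoenfeld gives HR 2.34 at 12 months and 2.22 at 24 months; Freedman gives 2.47 and 2.33. The detectable increase is thus roughly 120% to 150%.

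**The case against.** The best reply is that this is a one-word slip, with an increase written where a decrease was meant. On that reading the numerical result is correct and only the wording needs repair. This may be what happened, but the sentence is still false as written. Because it names toxicity, recurrence and death, a reader will take it as a statement about harm. Correcting the word alone would leave the plan with no power statement for harm.

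Reading 0.39 as control relative to HBO does not help either, since that implies a 156% increase, not 61%.

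It can also be said that little depends on the sentence. The primary endpoint is feasibility, with its own success rule in section 6.1. The 20 patients are set as four groups of five. Section 7.4 has a separate stopping rule for serious adverse events that does not use this figure. All of that is true: the error affects neither the sample size, nor the primary analysis, nor safety monitoring. It affects how the secondary comparison is read.

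Two further cautions stand:

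- Power to detect harm is not power for non-inferiority, which needs a margin. Correcting this sentence does not supply one.
- The 40% applies to a composite with a 6-month control median. Section 6.1 analyses events separately, and rarer events have less power. As an illustration, take the all-subject freedom from local recurrence in Table 1 as the control rate (85.5% at 1 year, 66.9% at 2 years) and ignore deaths. Power at HR 1.61 is then about 16% at 1 year and 25% at 2 years.

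**Conclusion.** The concern holds. The calculation supports 80% power for a 61% reduction in hazard, not for a 61% increase. For a 61% increase the power is 38% to 43% over 12 to 24 months of follow-up and cannot exceed about 44%, so such a rise would be missed more often than found. Harm reaches 80% power only at a hazard ratio of about 2.2 to 2.5, depending on formula and follow-up.

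The exact percentages rest on exponential times, no loss to follow-up and an unpaired test. The conclusion does not depend on the formula or the follow-up, because even 40 events in 40 patients leave power far below 80%. The plan's only power statement is wrong in the direction that matters for its non-inferiority objective, and it must be corrected.

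**What to change.** Replace the last sentence of section 6.2 with wording such as:

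> For the composite event-free survival endpoint (control median 6 months), 20 treated patients and 20 matched controls give 80% power at one-sided 0.05 to detect a hazard ratio of 0.39 or smaller, a reduction of 61% or more. For harm, 80% power is reached only at a hazard ratio of about 2.2 to 2.5 (Schoenfeld or Freedman formula, 12 to 24 months of follow-up). Power to detect a 61% increase is about 40%.

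The authors should also state which formula and follow-up produced 0.39, and say that power for individual events, such as local recurrence, may be lower.

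The cost is one sentence and a less favourable stated figure. It requires no extra patients, procedures or time.

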6.3 Subject Population(s) for Analysis

The study population will be any subject enrolled in the study.

7 Safety and Adverse Events

7.1 Definitions

Unanticipated Problems Involving Risk to Subjects or Others

Any incident, experience, or outcome that meets all of the following criteria:

- Unexpected in nature, severity, or frequency (i.e. not described in study-related documents such as the IRB-approved protocol or consent form, the investigators brochure, etc)

- Related or possibly related to participation in the research (i.e. possibly related means there is a reasonable possibility that the incident experience, or outcome may have been caused by the procedures involved in the research)
- Suggests that the research places subjects or others at greater risk of harm (including physical, psychological, economic, or social harm).

Adverse Event

An **adverse event** (AE) is any symptom, sign, illness or experience that develops or worsens in severity during the course of the study. Inter-current illnesses or injuries should be regarded as adverse events. Abnormal results of diagnostic procedures are considered to be adverse events if the abnormality:

- results in study withdrawal
- is associated with a serious adverse event
- is associated with clinical signs or symptoms
- leads to additional treatment or to further diagnostic tests
- is considered by the investigator to be of clinical significance

Solicited Adverse Event

A **solicited adverse event** is any adverse event that has been identified by the PI or co-PIs as potentially related to intracranial SRS and/or HBO treatments. Occurrence and severity of all solicited adverse events will be catalogued for all D12129 patients. These are enumerated in Attachment 14.6.

Serious Adverse Event

Adverse events are classified as serious or non-serious. A **serious adverse event** is any AE that is:

- fatal
- life-threatening
- requires or prolongs hospital stay
- results in persistent or significant disability or incapacity
- a congenital anomaly or birth defect
- an important medical event

Important medical events are those that may not be immediately life threatening, but are clearly of major clinical significance. They may jeopardize the subject, and may require intervention to prevent one of the other serious outcomes noted above. For example, drug overdose or abuse, a seizure that resulted in in-patient hospitalization, or intensive treatment of bronchospasm in an emergency department would typically be considered serious.

All solicited adverse events that do not meet any of the criteria for serious will be regarded as **non-serious solicited adverse events**.

Adverse Event Reporting Period

The study period during which solicited adverse events must be reported is defined as the period from the initiation of any study procedures to the end of the study treatment

follow-up. For this study, the study treatment follow-up is defined as the time following study treatment until the date of documented death, withdrawal of consent, or the end of the study, whichever occurs first.

Preexisting Condition

A preexisting condition is one that is present at the start of the study. A preexisting condition will be recorded as a solicited adverse event if the frequency, intensity, or the character of the condition worsens during the study period.

General Physical Examination Findings

At screening, any clinically significant abnormality will be recorded as a preexisting condition. At the end of the study, any new clinically significant findings/abnormalities that meet the definition of an adverse event must also be recorded and documented as an adverse event.

Post-study Adverse Event

All unresolved solicited adverse events will be followed by the investigator until the events are resolved, the subject is lost to follow-up, or the solicited adverse event is otherwise explained. At the last scheduled visit, the investigator will instruct each subject to report any subsequent event(s) that the subject, or the subject's personal physician, believes might reasonably be related to participation in this study. The investigator will notify the study sponsor of any death or adverse event occurring at any time after a subject has discontinued or terminated study participation that may reasonably be related to this study. The sponsor will also be notified if the investigator becomes aware of the development of cancer or of a congenital anomaly in a subsequently conceived offspring of a subject that has participated in this study.

Abnormal Laboratory Values

A clinical laboratory abnormality will be documented as an adverse event if any one of the following conditions is met:

- The laboratory abnormality is not otherwise refuted by a repeat test to confirm the abnormality
- The abnormality suggests a disease and/or organ toxicity
- The abnormality is of a degree that requires active management; e.g. change of dose, discontinuation of the drug, more frequent follow-up assessments, further diagnostic investigation, etc.

Hospitalization, Prolonged Hospitalization or Surgery

Any solicited adverse event that results in hospitalization or prolonged hospitalization will be documented and reported as a serious adverse event unless specifically instructed otherwise in this protocol. Any condition responsible for surgery will be documented as a serious adverse event if the condition meets the criteria for a solicited adverse event.

Neither the condition, hospitalization, prolonged hospitalization, nor surgery will be reported as an adverse event in the following circumstances:

- Hospitalization or prolonged hospitalization for diagnostic or elective surgical procedures for a preexisting condition. Surgery should **not** be reported as an outcome of an adverse event if the purpose of the surgery was elective or diagnostic and the outcome was uneventful.
- Hospitalization or prolonged hospitalization required to allow efficacy measurement for the study.
- Hospitalization or prolonged hospitalization for therapy of the target disease of the study, unless it is a worsening or increase in frequency of hospital admissions as judged by the clinical investigator.

